2.2.3 Daxdilimab

Daxdilimab is a human immunoglobulin (Ig)G1κ afucosylated mAb specific for human ILT7, a cell surface protein expressed by pDCs (Cho et al, 2008; Karnell et al, 2021; Rissoan et al, 2002). Daxdilimab binding to ILT7 on the surface of pDCs leads to recruitment of macrophages and natural killer (NK) cells, thus inducing apoptosis and reducing the number of pDCs. The afucosylation of daxdilimab is designed to improve the in-life potency of the molecule and to enhance the capacity for antibody-dependent cellular toxicity against pDCs.

2.2.4 Supportive Nonclinical Data

ILT7 is expressed only on the pDCs of humans and nonhuman primates; therefore, the cynomolgus monkey was selected as the relevant species for safety evaluation of daxdilimab.

Study 8311616 was a Good Laboratory Practice (GLP)-compliant, repeat-dose study in cynomolgus monkeys administered daxdilimab at 200 mg/kg intravenously (IV), 200 mg/kg SC, and 400 mg/kg SC once weekly for 4 weeks (5 doses). No daxdilimab-related clinical observations, body weight changes, ophthalmic observations, physical examination observations, macroscopic observations, or changes in blood pressure or electrocardiograms (ECGs) were observed. Daxdilimab administration had no clear or consistent group effects on clinical pathology parameters. Daxdilimab-related mild to moderate decreases of the group mean, absolute, and relative values of NK cells were observed in males given 200 or 400 mg/kg SC and in females given 200 mg/kg IV or SC and 400 mg/kg SC on Day 15 and Day 29 of the dosing phase. Daxdilimab-related pDC depletion was observed at all dose groups starting on Day 2 of the dosing phase. Plasmacytoid DC values were maintained at < 10% of mean baseline values in the majority of animals on Day 29. By Day 209, mean pDC values returned to baseline or approximately 50% of baseline in animals administered 200 mg/kg IV and 200 or 400 mg/kg SC, respectively. No other daxdilimab-related changes in peripheral blood immunophenotyping cells (total T cells, helper T cells, cytotoxic T cells, B cells, monocytes, and myeloid DCs) were observed in the blood, lymph nodes, and spleens of animals given \geq 200 mg/kg IV or SC. Daxdilimab had no effect on the ability to mount a T-cell-dependent antibody response to primary or secondary administration of antigen, indicating intact humoral immunity during daxdilimab administration.

Study 8338846 was a GLP-compliant, 6-month, repeat-dose study in cynomolgus monkeys. Daxdilimab was administered once weekly via SC injection for 6 months (a total of 28 doses) at doses of 200 and 400 mg/kg/week. There were no daxdilimab-related clinical, ophthalmic, body weight, or physical observations; no changes were observed in cardiac measurements or observations, or clinical or anatomic pathology. In addition, there were no daxdilimab-related effects on reproductive organs or assessments. No daxdilimab-related changes were noted for IgG, IgM, IgA, IgE, or peripheral blood immunophenotyping, except pDCs as expected by pharmacology. Daxdilimab-related depletion of mean absolute and relative values for pDCs was noted on Day 2 of the dosing phase in animals administered 200 or 400 mg/kg/week. The only daxdilimab-related observation was a minor increase in mononuclear cell and macrophage infiltrates at the injection sites of animals administered daxdilimab compared with controls. These increases were not dose dependent, and partial reversibility was noted in recovery animals.

Based on these results, the no-observed-adverse-effect-level is 200 mg/kg when given via IV infusion and 400 mg/kg/week when given by SC injection. Additional details of these and other nonclinical studies are included in the Investigator's Brochure (IB).

2.2.5 Supportive Clinical Data

Daxdilimab has been investigated in Phase 1 single-ascending dose (SAD) and Phase 1b multiple-ascending dose (MAD) clinical studies in subjects with autoimmune diseases (Studies D6080C00001 and VIB7734.P1b.S1, respectively). Study D6080C00001 has been completed. Study VIB7734.P1b.S1 has a locked database, and all study-site visits have been completed.

2.2.5.1 Phase 1 Single-Ascending Dose Study in Subjects with Autoimmune Diseases

A Phase 1 SAD study (Study D6080C00001) of daxdilimab enrolled subjects with any of 5 autoimmune diseases: dermatomyositis, polymyositis, SLE, Sjögren's syndrome, and systemic sclerosis. Single SC doses of daxdilimab (1, 5, 15, 50, or 150 mg) or placebo were administered to 36 subjects ([Karnell et al, 2021](#)). No safety, tolerability, or immunogenicity issues were identified. Pharmacodynamic (PD) analysis showed a dose-dependent reduction in pDC levels, which was observable on Day 2 (one day after dosing on baseline [Day 1]) and maximal on Day 15 ([Karnell et al, 2021](#)). The duration of pDC reduction was largely dose dependent and was reversible in all cases. Median pDC levels returned to above 50% of baseline at the following time points for each cohort: 1 mg: Day 29; 5 mg: Day 57; 15 mg: Day 57; and 50 mg: Day 85. The time to return to above 50% of baseline could not be determined for 150 mg, since subjects met protocol-defined minimum absolute pDC number repletion criteria and exited the study before this occurred.

2.2.5.2 Phase 1b Multiple-Ascending Dose Study in Subjects with Autoimmune Diseases

In a single-blind (subjects and site blinded, Sponsor unblinded), Phase 1b MAD study (Study VIB7734.P1b.S1), daxdilimab or placebo was administered SC every 4 weeks (Q4W) for 3 doses to a total of 31 subjects in 3 cohorts ([Karnell et al, 2021](#)). In the first cohort, 8 subjects with any of 6 autoimmune diseases (dermatomyositis, polymyositis, SLE, cutaneous lupus erythematosus (CLE), Sjögren's syndrome, or systemic sclerosis) were randomized to daxdilimab (5 mg SC) or placebo in a 3:1 ratio. The second and third cohorts enrolled subjects with active cutaneous lupus, defined as a Cutaneous Lupus Erythematosus Disease Area and Severity Index-Activity (CLASI-A) score ≥ 8 . In the second cohort, 12 subjects were randomized to daxdilimab 50 mg SC or placebo in a 2:1 ratio. In Cohort 3, 11 subjects were randomized to daxdilimab 150 mg SC or placebo in a 2:1 ratio.

A reduction in blood pDC level was observed at the first time point after dosing (Week 1) and persisted through the 3-month treatment period. A high type I IFN signature was present at baseline in 18 of 23 subjects (78%) in Cohorts 2 and 3. The median change in IFN signature at Month 3 was -54% in the daxdilimab 50 mg group, -83% in the daxdilimab 150 mg group, and +8% in the placebo group. On the skin biopsy at Month 3, the median change in pDC density was -87% for the 50 mg group, -99% for the 150 mg group, and -14% for the placebo group. The median change in CLASI-A from baseline to Month 3 was -5 in the 50 mg group, -9.5 in the 150 mg group, and -5 in the placebo group ([Karnell et al, 2021](#)). At Month 3, a $\geq 50\%$ improvement in CLASI-A was observed in 38% of subjects who received 50 mg daxdilimab, 75% of subjects who received 150 mg daxdilimab, and 29% of subjects who received placebo. The proportion of subjects with an adverse event (AE) was similar in the daxdilimab and placebo groups (73% versus 67%, respectively). No serious AEs (SAEs) or other clinically important AEs occurred in daxdilimab-treated study subjects ([Karnell et al, 2021](#)).

2.3 Benefit/Risk Assessment

More detailed information about the known and expected benefits and risks and reasonably expected AEs of daxdilimab may be found in the IB.

2.3.1 Risk Assessment

There are no important identified risks for daxdilimab. Important potential risks for daxdilimab may include viral infection and viral reactivation, opportunistic infection, malignancy, and hypersensitivity reactions, including anaphylaxis. More detailed descriptions of these potential risks are included in the IB.

Hypersensitivity reactions, including anaphylaxis, are a risk associated with administration of biologic drugs. Definitions for these reactions can be found in Appendix 5, [Section 10.5](#).

Appropriate drugs and medical equipment to treat acute anaphylactic and serious hypersensitivity reaction must be immediately available at study sites, and study personnel must be competent to recognize and treat anaphylaxis. In addition, subjects will be monitored after investigational product (IP) administration for immediate drug reactions. Hypersensitivity reactions and anaphylaxis have not been observed in Phase 1 SAD and Phase 1b MAD studies.

2.3.1.1 COVID-19 Risk Assessment

An additional risk of study participation includes potential exposure of the subject to severe acute respiratory syndrome coronavirus 2 (SARS-CoV-2), the virus that causes coronavirus disease 2019 (COVID-19), by visiting the study site. Sites must have a plan in place to minimize this risk. Although testing for COVID-19 prior to Dose 1 is not required, the Investigator may choose to have this test performed locally in accordance with his/her judgment based on subject risk. This test is not provided through the study's central laboratory, because the result of a test at Visit 1 would not be appropriately timed to be relevant to Dose 1. Such testing is not required.

To minimize risk to study subjects, study sites will be activated to initiate subject enrollment only after review of local COVID-19 disease incidence, prevalence, containment measures, availability of healthcare resources, ability to monitor site activities, and the presence of a site plan to minimize subject exposure to SARS-CoV-2 during site visits have been confirmed.

There are no data on the effect of daxdilimab on the risk for infection with SARS-CoV-2 or on the severity of COVID-19 illness.

The current available evidence does not suggest a difference in COVID-19 infection risk in persons with SLE compared to the general population except for what is known about the increased risk that may be associated with comorbid disease and use of immunosuppressive treatment.

The Investigator will assess the benefit-risk for each individual subject for determination of suitability for enrollment based on known risk factors for COVID-19 severity and possible or known exposure to SARS-CoV-2.

Because of the evolving spread and containment measures of COVID-19, ongoing risk assessment will be required of participating study sites and Investigators.

2.3.2 Benefit Assessment

Daxdilimab is being developed for the treatment of multiple autoimmune disorders in which pDCs are believed to contribute to their pathogenesis, including alopecia areata, dermatomyositis, discoid lupus erythematosus, LN, and SLE. The available nonclinical safety profile for daxdilimab is supportive of administration in subjects with SLE at exposures that do

not exceed those considered to be non-adverse to animals in toxicity studies performed per GLP guidelines ([Section 2.2.4](#)). In addition, the emerging clinical data available from two Phase 1 studies (Study D6080C00001 [[Section 2.2.5.1](#)] and Study VIB7734.P1b.S1 [[Section 2.2.5.2](#)]) demonstrates an acceptable safety profile, and no adverse drug reactions have been identified.

Given the daxdilimab mechanism of action ([Section 2.2.3](#)), the unmet need for patients with SLE ([Section 2.2.2](#)), and the favorable emerging data from the Phase 1 studies ([Section 2.2.5](#)), it is hypothesized that treatment with daxdilimab in study subjects with moderately-to-severely active SLE may result in maintenance or improvement in their condition as a result of participating in this study. Since all subjects in the study will receive unblinded, open-label daxdilimab irrespective of their assigned treatment in the RECAST SLE study, all study subjects have the potential to benefit from participating in this OLE study.

2.3.3 Overall Benefit-Risk Conclusion

To date, a relatively small number of subjects have been exposed to daxdilimab across the ongoing clinical studies, so a full evaluation of risk/benefit is limited at present. However, no clinically important safety issues have emerged that preclude further evaluation of daxdilimab in the relevant clinical study populations at the doses chosen for this study, and the benefit-risk evaluation remains favorable.

Considering the measures taken to minimize risk to subjects participating in this study, the potential risks identified in association with daxdilimab are justified by the anticipated benefits that may be afforded to study subjects with SLE.

3 OBJECTIVES AND ENDPOINTS

The objectives and endpoints to be evaluated in this study are provided in Table 2.

Table 2 Primary, Secondary, and Exploratory Objectives

Objectives	Endpoints
Primary Objective	
To evaluate the long-term safety and tolerability of 200 mg Q12W daxdilimab	
Incidence of AEs, SAEs, and AESIs
Secondary Objectives	
To characterize the PK, PD, and immunogenicity of daxdilimab	
Daxdilimab concentrations, change in pDCs, and ADA rate
Exploratory Objectives	

Table 2 Primary, Secondary, and Exploratory Objectives

Objectives	Endpoints

ADA = anti-drug antibodies; AE = adverse event; AESI = AE of special interest;

PD = pharmacodynamic(s); pDC = plasmacytoid dendritic cell; [REDACTED];
PK, pharmacokinetic(s); Q12W = every 12 weeks; RECAST SLE = Phase 2 Randomized, Double-Blind,
Placebo-Controlled Efficacy and Safety Study of daxdilimab for the Treatment of Moderate to Severely
Active Systemic Lupus Erythematosus; [REDACTED]
[REDACTED] SAE = serious AE; SLE = systemic
lupus erythematosus; [REDACTED]

4 STUDY DESIGN

4.1 Overall Design

Protocol HZN-DAX-204 is an open-label study designed to evaluate the long-term safety and tolerability of 200 mg daxdilimab Q12W in subjects with SLE. The study design is provided in [Section 1.2 \(Figure 1\)](#).

Irrespective of their assigned treatment in the RECAST SLE study, all subjects participating in the SLE OLE will be treated with daxdilimab 200 mg SC Q12W in addition to their standard-of-care SLE therapy.

Once a subject has completed the treatment period (through Week 48) of the RECAST SLE study, signed the informed consent form (ICF), and met all study eligibility criteria, he/she may be enrolled in the OLE study. To allow for the continuous dosing of the subjects, the start of this OLE study should occur immediately after the completion of the RECAST SLE treatment period (ie, first OLE dosing [Day 1] coinciding with Week 48/Visit 14 of the RECAST SLE study). Any exceptions to this enrollment date must be reviewed and approved by the Medical Monitor before any subject is allowed to enroll after the Week 48/Visit 14 of the RECAST SLE study. ([Section 5.5](#)). Subjects will be treated with open-label daxdilimab 200 mg Q12W SC for 48 weeks. After the treatment period (Week 0 to Week 48), the subjects will enter an 8-week safety follow-up (SFU) period (Week 48 to Week 56).

Subjects who permanently discontinue IP at any point but who **do not** withdraw consent of study participation will complete the Study Week 48/early termination (ET) visit as soon as possible after IP discontinuation and then enter the SFU period as indicated in the schedule of assessments (SoA) ([Table 1](#)). Participants will not automatically be removed from the study if any administration of IP is missed.

The study will be conducted on an outpatient basis. For scheduled study visits, subjects will come to the study sites on 7 occasions: Weeks 0 [Day 1], 12, 24, 36, 48, 52, and 56. In addition, telehealth visits (phone or video call) will be performed on 8 occasions (Weeks 4, 8, 16, 20, 28, 32, 40, and 44) to assess the subject's current disease status, the OGC tapering schedule, safety, and concomitant medications ([Section 8.1](#)). For all IP administrations, daxdilimab will be

administered by study-site staff at the study site, and the subject will be observed for at least 60 minutes after the first and second doses (Day 1 and Week 12) are administered to each subject. Blood collection and study assessments will be performed at the times specified in the SoA ([Table 1](#)).

An external, independent Safety Data Monitoring Committee (SDMC) will be responsible for safeguarding the interests of study subjects via review of accumulating safety data and for supporting study integrity and interpretability based on their review of ongoing study conduct ([Appendix 1, Section 10.1.5](#)).

The primary objective of this OLE study is to evaluate the long-term safety and tolerability of 200 mg daxdilimab Q12W in adult subjects with moderately-to-severely active SLE. This will be assessed by summarizing AEs, SAEs, and AEs of special interest (AESI).

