4.4 End-of-Study Definition

An individual subject will be considered to have completed the study if the subject was followed up through the last protocol-specified visit, regardless of the number of doses of IP that was received.

Subjects will be considered not to have completed the study if consent was withdrawn ([Section 7.2](#)) or the subject was lost to follow-up ([Section 7.3](#)).

The end of the study (“study completion”) is defined as the date of the last protocol-specified visit/assessment for the last subject in the study.

Information regarding site/study termination or suspension is found in Appendix 1, [Section 10.1.12](#).

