7.1 Discontinuation of Investigational Product

An individual subject will not receive any further IP if any of the following occur in the subject:

- Receipt of any medications or therapies in [Section 6.9.3](#).
- A Grade 3 or higher allergic reaction to the IP.
- A Grade 3 or higher infection considered related to the IP.
- Other AE that contraindicates further dosing in the opinion of the Investigator and/or the Sponsor, Medical Monitor, and/or the SDMC.
- Withdrawal of consent from further treatment with IP.
- Subject is determined to have met one or more of the exclusion criteria or failed to meet all the inclusion criteria for study participation and there is a potential safety risk associated with continuation identified upon consultation with the Medical Monitor.
- Pregnancy or a decision to become pregnant.
- Any of the following liver function abnormalities:
 - Alanine aminotransferase (ALT) or aspartate aminotransferase (AST) $\geq 8 \times$ upper limit of normal (ULN).
 - ALT or AST $\geq 5 \times$ ULN for more than 2 weeks.
 - ALT or AST $\geq 3 \times$ ULN and total bilirubin $\geq 2 \times$ ULN or international normalized ratio ≥ 1.5 without alternative explanation.
 - ALT or AST $\geq 3 \times$ ULN with the appearance of fatigue, nausea, vomiting, right upper quadrant pain or tenderness, fever, rash, and/or eosinophilia ($\geq 5\%$).

Subjects who permanently discontinue IP at any point but who **do not** withdraw consent of study participation will complete the Study Week 48/ET visit as soon as possible after IP discontinuation and then enter SFU period unless the subject withdraws consent of study participation (as described in Section 7.2) or the subject is lost to follow-up (Section 7.3).

Appendix 4, [Section 10.4](#) describes the process to be followed to identify and appropriately report potential Hy's Law cases and Hy's Law cases.

Follow the SoA ([Table 1](#)) for data to be collected at the time of discontinuation of IP and follow-up and for any further evaluations that need to be completed.

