7.3 Lost to Follow-up

A subject will be considered lost to follow-up if the subject repeatedly fails to return for scheduled visits and is unable to be contacted by the study site.

Subjects will be considered lost to follow-up only if no contact has been established by the time the study is completed such that there is insufficient information to determine the participant's status on Day 393 (Visit 15).

The following actions must be taken if a subject fails to return to the clinic for a required study visit:

- The site must attempt to contact the subject and reschedule the missed visit as soon as possible, counsel the subject on the importance of maintaining the assigned visit schedule and ascertain whether the subject wishes to and/or should continue in the study.
- Before a subject is deemed lost to follow-up, the Investigator or designee must make every effort to regain contact with the subject with 3 documented attempts at contact (with one documented attempt being a registered letter/certified mail):
 - Registered letter/certified mail
 - Phone calls, text messages, or emails
 - Consulting publicly available sources, if allowed by local regulations, to determine the status of the subject.

These contact attempts should be documented in the subject's medical record.

- Should the subject continue to be unreachable, the subject will be considered to have withdrawn from the study.

“Lost to follow-up” as a reason for study discontinuation must be documented by time and date of telephone calls, emails, text messages, numbers called, individuals spoken to if not the subject, documentation that a certified/registered letter was sent, and documentation of publicly available sources that were consulted.

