9.5 Sample Size Determination

Sample size determination is based on the number of subjects who have completed the treatment period of Study VIB7734.P2.S1 (RECAST SLE). A total of 195 subjects have been randomized in the RECAST SLE study. Assuming that 20% of subjects will prematurely discontinue treatment, there will be a total of approximately 156 subjects who will be eligible for this long-term safety study.

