4.8 Exploratory Efficacy Analyses

4.9 Safety Analyses

4.9.1 Adverse Events

Adverse events (AEs) collected in this OLE study will be summarized separately using the OLE safety analysis set and together with the AEs collected in study RECAST SLE using the any daxdilimab analysis set overall and by treatment group. Table 4 presents the definition of treatment-emergent adverse event (TEAE) for reporting purposes.

Study	Definition
OLE	A TEAE is defined as any AE with an onset date on or after the first dose date in the OLE study.

Study	Definition
OLE + RECAST SLE (Any daxdilimab exposure)	A TEAE is defined as any AE with an onset date on or after the first daxdilimab dose date (either in OLE or RECAST SLE study)

Table 4Definition of TEAEs

AEs will be coded using the most recent version of MedDRA. All TEAEs will be summarized overall and by MedDRA system organ class (SOC) and preferred term (PT), by severity and by relationship to daxdilimab. Specific AEs will be counted once for each participant for calculating rates, but all events will be presented in participant listings. In addition, if the same AE occurs multiple times within a particular participant, the highest severity and level of causality will be reported.

In addition, since the duration of exposure to daxdilimab is shorter for the participants who received placebo in the RECAST SLE study, the PYE adjusted incidence rate for the number of participants who experienced TEAE will be included in the combined summary of OLE + RECAST SLE using any daxdilimab analysis set. Refer to Section 4.6 for definition of PYE.

An overall summary table will be showing the number and percentage of participants with at least one event in any of the following categories:

- TEAE
- Treatment-emergent serious adverse event (TESAE)
- TEAE resulting in death
- Grade 3 or higher TEAE using CTCAE v5.0
- TEAE leading to discontinuation of daxdilimab
- Serious and/or grade 3 or higher TEAE
- Daxdilimab related TEAE
- Daxdilimab related TESAE

The following AE summaries will also be provided by SOC and PT:

- TEAEs
- TEAEs resulting in death
- Grade 3 or higher TEAEs using CTCAE v5.0
- TEAE leading to discontinuation of daxdilimab
- Daxdilimab related TEAE
- TESAEs
- Daxdilimab related TESAE

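### The protocol does not fix when follow-up ends after an early IP stop, and the OLE-only AE percentages make no allowance for unequal follow-up

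*Protocol*

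**What the plan says.** **Path after stopping.** Protocol 4.1 has such a subject complete the Week 48/ET "visit as soon as possible after IP discontinuation and then enter the SFU period as indicated in the schedule of assessments". Section 7.1 repeats this and adds: "Follow the SoA ([Table 1](#)) for data to be collected at the time of discontinuation of IP and follow-up". Table 1 dates the two SFU visits (Visits 14 and 15) only as Days 365 and 393, and 4.1 labels the SFU Week 48 to Week 56. The synopsis describes the same period by length, as two visits four weeks apart over 8 weeks. Neither description is expressly tied to the ET visit of an early stopper. Nothing keeps that subject on the remaining 12-weekly or telehealth visits.

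**Completion and loss.** Under 4.4 a subject has completed the study if "followed up through the last protocol-specified visit, regardless of the number of doses of IP that was received". Only withdrawn consent or loss to follow-up makes a non-completer. Section 7.3 judges loss to follow-up by status on Day 393, which it labels Visit 15.

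**AE collection.** Protocol 8.4.4 collects AEs and SAEs up to the final study visit. After that, the investigator need only notify SAEs that come to notice and are considered reasonably related.

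**Analysis.** SAP 4.9.1 states: "Adverse events (AEs) collected in this OLE study will be summarized separately using the OLE safety analysis set". The overall summary is the number and percentage of participants with at least one event. The OLE treatment-emergent definition has a start (first OLE dose) but no end. The rate adjusted for person-years of exposure (PYE) is specified only for the combined OLE + RECAST SLE summary, because former placebo subjects have shorter exposure. SAP 4.6 ends PYE 28 days after the last dose.

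**The concern.** The primary endpoint is the incidence of AEs, SAEs and AESIs, and the objective is long-term safety. A crude percentage is easy to interpret when everyone is observed for about the same time. If the SFU visits are timed from ET, observation after the first OLE dose runs from little more than 8 weeks to 56 weeks, and the percentage depends on how many subjects stop and when.

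Stopping is unlikely to be random. The triggers in 7.1 include Grade 3 or higher allergic reactions, related Grade 3 or higher infections, liver abnormalities, other AEs and receipt of a 6.9.3 therapy. Some AESIs, such as malignancy and opportunistic infection, may appear late.

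If the visits instead stay on Days 365 and 393, follow-up is not shortened. A subject with ET at Week 12 then has no scheduled contact until Week 52, 40 weeks later. Sites could follow either reading, so follow-up could differ from site to site for reasons unrelated to the subjects.

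**Working it through.** **1. The plan's own figure.** Protocol 9.5 starts from the 195 randomised in RECAST SLE, takes off 20% for early stopping there, and concludes: "there will be a total of approximately 156 subjects who will be eligible for this long-term safety study". 195 × (1 − 0.20) = 156, which reproduces. The 20% is attrition in RECAST SLE. Neither document gives an OLE stopping rate, and there is no hypothesis test, alpha or power to check.

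**2. Assumptions.** N = 156. A fraction d = 10%, 20% or 30% stops IP, with stops spread evenly over Weeks 0–48. ET takes place when IP stops, and the subject exits 8 weeks later. All others are followed for 56 weeks. The event hazard is constant.

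**3. One subject.** ET at Week 4, 12, 24 or 36 gives exit at Week 12, 20, 32 or 44, which is 44, 36, 24 or 12 weeks short of Week 56.

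**4. Person-time.** A stopper's mean follow-up is 24 + 8 = 32 weeks, so 24 weeks are lost on average. Full follow-up is 156 × 56 × 7/365.25 = 167.4 person-years. Loss = 156 × d × 24 × 7/365.25, and as a share d × 24/56.

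**5. Participants with at least one event.** For a 56-week risk p, λ = −ln(1 − p)/56. Among stoppers the expected percentage is the mean of 1 − exp[−λ(T + 8)] over T uniform on 0–48. For p = 10% this is 5.8%. Crude percentage = (1 − d) × 10% + d × 5.8%.

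| d | Mean follow-up (weeks) | Person-years lost | Share | Crude %, equal hazards (full follow-up 10%) | Stoppers' hazard doubled: crude vs full |
|---|---|---|---|---|---|
| 10% | 53.6 | 7.2 | 4.3% | 9.6 | 10.1 vs 10.9 |
| 20% | 51.2 | 14.4 | 8.6% | 9.2 | 10.2 vs 11.8 |
| 30% | 48.8 | 21.5 | 12.9% | 8.7 | 10.4 vs 12.7 |

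With equal hazards, across the same stopping range, the shortfall is 0.2–0.6 points for an assumed 5% risk and 0.8–2.5 points for 20%.

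**6. Can the existing PYE serve as denominator?** Reading SAP 4.6 as last dose + 28 − first dose + 1, a completer dosed on Days 1 and 337 has 337 + 28 − 1 + 1 = 365 days, against 393 days of AE collection. A subject who stops after one dose has 1 + 28 − 1 + 1 = 29 days, although AEs are collected until the last visit. PYE is therefore not the time over which the AEs are counted.

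**The case against.** **Truncation is not the only reading.** Section 4.1 sends stoppers to the SFU as laid out in Table 1, which shows fixed days. This stands: what is established is wording that must be reconciled, with shortened follow-up as the more natural consequence.

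**The percentage may be a legitimate target.** Completers are dosed at Week 48 and followed for 8 weeks. A stopper with ET at Week 12 and no dose that day is followed for about 20 weeks after the last dose. Measured from the last dose, stoppers get about as much follow-up as completers or more, so the percentage is coherent as treatment period plus 8 weeks. AEs much later may also reflect therapies started after IP. This stands too: a flat claim of downward bias presumes a 56-week target that the SAP does not state. The fair criticism is that the SAP states no target window.

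**Section 7.3 is not contradicted.** A reader might infer that a subject who exits at Week 20 breaks the Day 393 rule. Loss to follow-up also requires repeated failure to return for scheduled visits, and a stopper who attends Visit 15 has not failed to return. The Day 393 label simply does not fit that subject if visits are timed from ET.

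**Some of this is already visible.** SAP 4.5 separates completed treatment, discontinued treatment and completed trial. SAP 4.6 tabulates OLE person-years and duration bands. OLE AEs also enter the combined adjusted summary. None of these gives an OLE-only rate over observed time, or shows how many trial completers had shortened follow-up.

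**Conclusion.** The point holds as a gap in specification with a modest numerical effect. The timing of SFU visits after an early stop is ambiguous. On the more natural reading follow-up is unequal, and the primary OLE-only summary does not account for it. Under the assumptions above, 4.3–12.9% of person-time is unobserved and a 10% participant risk shows as about 9.6–8.7%. Stopping rate, stopping times, event risk and hazard are all assumptions. If Visits 14 and 15 stay on fixed days, the shortfall disappears and sparse contact takes its place.

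Two stronger inferences should be resisted.

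- A reader might quote an 18% under-count. That comes from 20% stopping and a threefold event rate in stoppers: 1 − (0.8 × 56 + 0.2 × 32 × 3)/(0.8 × 56 + 0.2 × 56 × 3) = 1 − 64/78.4 = 18.4%. It is a loss of events, whereas the planned summary counts participants, and a subject who stops because of an SAE or AESI is already counted for that category. The threefold rate has no source in the documents.
- A reader might conclude that stoppers must be contacted by telehealth to Day 393. That is a design choice, and the telehealth slots end at Week 44, so they could not carry it.

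**What to change.** 1. **SAP 4.9.1:** beside the OLE-only percentages for TEAEs, SAEs and AESIs, report the number of participants with an event per observed person-time, counted from first OLE dose to first event or last study contact. Do not reuse the PYE of SAP 4.6. This adjusts for length of follow-up under a roughly constant rate; it does not correct for stoppers being a different-risk group.
2. **Protocol 4.1, 7.1, 7.3 and Table 1:** reconcile how Visits 14 and 15 are anchored for a subject who stops IP early, and state the OLE AE follow-up window so that the percentage has a defined target.
3. **SAP 4.5:** within completed trial, show separately the subjects who finished the SFU after stopping IP early.

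The cost is one extra column in the OLE AE tables, one disposition row and a wording clarification. The analysis changes use data already collected. No new visits are required.
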